#### 5.10.4.2 Other Notifiable Events

Pregnancy is the only additional notifiable event that requires expedited reporting as detailed in Sections 5.10.4.3 and 5.10.4.4.

#### 5.10.4.3 Procedures to follow in the event of female participants becoming pregnant

A pregnancy test is conducted for all females of childbearing age and the results are recorded in the medical notes before enrolling a volunteer to the CNGB3 or CNGA3 trial. Females with a positive pregnancy test at the time of planned ATIMP administration are to be excluded from the trial prior to administration of the ATIMP.

Participants are instructed to use barrier contraception for 12 months after ATIMP administration. However, it is difficult to exclude entirely that a participant might become pregnant after administration of the ATIMP. In the unlikely event that a participant is found to be pregnant in the 12 months following ATIMP administration, the participant's GP will be notified that she is participating in a gene therapy trial and that, although the risks involved are minimal, there is a chance of gene transfer to the unborn child. With the participant's consent, we will ask the GP/obstetrician to provide us with regular reports about the pregnancy until delivery. The pregnancy will be reported to The PV service provider on a pregnancy report form within 24 hours of the investigator becoming aware of the event, following the instructions on the pregnancy form. The participant will continue to be followed-up until outcome of the pregnancy. However, if the participant is unable or unwilling to participate further in the study, she will be encouraged to continue clinical monitoring visits to assess ocular health.

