# 5.4 Participation

#### 5.4.1 Protocol Defined Clinical Schedule

#### 5.4.1.1 Follow Up Assessments

Both safety and efficacy of the ATIMP will be evaluated at various time points, between 6 months and 5 years after ATIMP delivery, in this study. Evaluation will occur primarily by ocular assessments that will be read at independent reading centres in the UK and USA. Clinical assessments will be scheduled over a consecutive period of up to 3 days for each visit. The nature and schedule (Section 5.6, Assessment Schedule) of the follow up assessments is described below.

In addition, a serology test sample for evaluation of immune response will be drawn at each visit in this study (described as serology test in the Assessments Schedule table in Section 5.6).

There is wide variability in the ability of children of different ages to undertake some of the proposed tests; the evaluations for children will be restricted to those tests that they are able to perform reliably.

Tests that will be performed in all participants are:

- Ocular examination
- Colour fundus photography
- Spectral Domain Optical Coherence Tomography (SD-OCT)
- Fundus Autofluorescence Imaging (FAF)
- Best corrected visual acuity
- Full-field electroretinography (ERG)
- Pattern electroretinography (PERG)
- Serology tests (AAV8 antibody and transgene antibody testing)
- Light-sensitivity testing/Photoaversion testing
- Contrast sensitivity
- Static perimetry
- Quality of Life

Tests that will be performed in all patients unless not possible due to lack of patient co-operation or equipment/facilities are:

- Reading assessment
- Colour vision testing
- Adaptive optics (AO) imaging
- Pregnancy test (up to 12 months)
- Full Field Stimulus Testing (FST)

Additional investigations may be performed for appropriate clinical management of any adverse events. Further details of clinical assessments can be found in the Gene Therapy for Achromatopsia (CNGB3 and CNGA3) study manuals. Images taken at all timepoints will be sent for independent reading and analysis at centres in both the UK and the US and to the sponsor and research

development partners. ERG assessments may be performed under general anaesthetic where considered appropriate.

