# 5.6 Assessment Schedule

Timings are since ATIMP administration.

	CNGB3/
	CNGA3
	M3¹
Visit no.	
Informed consent	•
Medical history	
Pregnancy test	
Adverse event review	
Concomitant medication review	
Serology test (AAV8 antibody and	
Transgene antibody testing)	
QoL questionnaires (IVI and EQ5D-	
5L)	
Static perimetry	
Visual acuity	
Contrast sensitivity	
Reading speed	
Colour vision	
Ocular examination	
Fundus photography	
Optical coherence tomography	
Adaptive optics imaging	
Fundus autofluorescence	
Full field electroretinography 	
Pattern electroretinography 	
Photoaversion assessments 	
Full Field Stimulus Testing 	
Flexibility of schedule (±days)	

M9	M12	M18	M24	M36	M48	M60
1	2	3	4	5	6	7
•						
•	•	•	•	•	•	•
•	•					
•	•	•	•	•	•	•
•	•	•	•	•	•	•
•	•	•//	•	•	•	•
	• /		•	•	•	•
•	•	•	•	•	•	•
•/	•	•	•	•	•	•
•	•	•	•	•	•	•
•	•	•	•	•	•	•
•	•	•	•	•	•	•
•	•	•	•	•	•	•
•	•	•	•	•	•	•
•	•	•	•	•	•	•
•	•	•	•	•	•	•
•	•	•	•	•	•	•
	•		•	•	•	•
	•		•	•	•	•
	•		•	•	•	•
•	•	•	•	•	•	•
21	21	60	60	60	60	60

<sup>1 Initial consent for the long term follow up study will be obtained at the 3 or 6 month visit of the active CNGB3 or CNGA3 trial (or anytime thereafter).

<sup>2 Electroretinography testing will be discontinued after M12 if responses remain undetectable

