# 5.10.4.4 Procedures to follow in the event of the partners of male participants becoming pregnant

Participants are instructed to use double barrier contraception for 12 months after ATIMP administration. However, it is difficult to exclude entirely that the partner of a participant might become pregnant after administration of the ATIMP. In the unlikely event that the partner of a participant is found to be pregnant in the 12 months following ATIMP administration, the participant's GP will be notified that he is participating in a gene therapy trial and that, although the risks involved are minimal, there is a chance of gene transfer to the unborn child. With the participant's consent, we will contact the partner to ascertain the status of the pregnancy and the outcome. The pregnancy will be reported to The PV service provider on a pregnancy report form within 24 hours of the investigator becoming aware of the event, following the instructions on the pregnancy form.

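### Read literally, the pregnancy reporting rule turns on discovery within 12 months of dosing, so it omits pregnancies conceived in that period but found later, including by a Month 12 test held late within its permitted window.

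*Protocol*

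**What the plan says.** Protocol 5.10.4.3 covers female participants. It states the contraception instruction ("Participants are instructed to use barrier contraception for 12 months after ATIMP administration") and then sets the condition "In the unlikely event that a participant is found to be pregnant in the 12 months following ATIMP administration". GP notification and, with consent, regular reports until delivery follow from that condition. So does the expedited report: the site must send a pregnancy form to the pharmacovigilance provider no later than 24 hours after the investigator learns of it. The reason given is a small chance that the transferred gene reaches the fetus.

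Protocol 5.10.4.4 applies the same limit to male participants, where "the partner of a participant is found to be pregnant in the 12 months following ATIMP administration".

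Protocol 5.10.4.2 adds no trigger of its own: "Pregnancy is the only additional notifiable event that requires expedited reporting as detailed in Sections 5.10.4.3 and 5.10.4.4".

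The table in Protocol 5.6 counts time from ATIMP administration. It marks pregnancy tests at Month 9 and Month 12 only, each with a visit window of ±21 days, and section 5.4.1.1 likewise ends testing at 12 months. No test is scheduled for partners. SAP 3.4.3 says only that pregnancy data will be listed. Neither document sets a trigger by conception date.

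**The concern.** A 12-month limit can attach to conception or to discovery. The contraception instruction and the stated worry about the fetus both concern conceptions in the first 12 months. The reporting clause, on its natural reading, concerns discoveries in the first 12 months. Discovery always follows conception, so the two sets differ at the end of the period: late conceptions within the 12 months tend to come to light after it.

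The primary objective is longer-term safety, and participants are followed to Month 60. A site may therefore learn of such a pregnancy at a later visit and, following the text, have no stated duty to send the pregnancy form within 24 hours or to follow the outcome. Those are the pregnancies the 12-month period was presumably meant to cover.

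**Working it through.** The plan gives no figure to reproduce. The check is day arithmetic plus a comparison of sections.

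**Inputs**
- Reporting limit: 12 months from administration (Protocol 5.10.4.3, 5.10.4.4), taken as day 365.
- Contraception period: 12 months from administration (same sections).
- Last scheduled test: Month 12, ±21 days, same time origin (Protocol 5.6).
- Lag from conception to a positive test: not in the documents. Assumed at 10, 14, 28 and 42 days to show a range.

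**Step 1: Month 12 window against the reporting limit**
- Earliest permitted visit: 365 − 21 = day 344.
- Latest permitted visit: 365 + 21 = day 386.
- Permitted days: 386 − 344 + 1 = 43.
- Permitted days after the limit: 386 − 365 = 21 (days 366 to 386), and 21/43 = 49%.

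A positive result on any of those 21 days comes from a test the protocol requires, held on time, yet lies outside the literal trigger. This step needs no outside assumption. The 49% is a share of permitted visit days, not of visits or pregnancies.

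**Step 2: conceptions that cannot be found by day 365**

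A pregnancy conceived on day *d* (1 to 365) cannot be found within the limit if *d* + lag > 365. The number of such days equals the lag.

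| Assumed lag (days) | Conception days that cannot be found by day 365 | Share of 365 | Of these, detectable at a day-386 test | Not detectable even then |
|---|---|---|---|---|
| 10 | 10 | 2.7% | 10 | 0 |
| 14 | 14 | 3.8% | 14 | 0 |
| 28 | 28 | 7.7% | 21 | 7 |
| 42 | 42 | 11.5% | 21 | 21 |

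Earlier conceptions that are simply noticed late add to this. The shares are of calendar days and say nothing about how many pregnancies occur.

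**Step 3: do other sections close the gap?**
- Protocol 5.10.4.2 defers to the two limited sections and so inherits their limit.
- Protocol 5.6 has medical history and adverse event review at every visit to Month 60. A site may hear of a pregnancy this way, but the lists of adverse events in 5.10.4.1 do not name pregnancy.
- Protocol 5.10.4.5 extends recording to the pregnancy outcome. It governs how long recording lasts, not which pregnancies must be reported.
- Protocol 5.10.4.1 makes a birth defect a serious event. That catches an adverse outcome, not the pregnancy.

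None of these requires an uneventful pregnancy found after 12 months to be reported.

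**The case against.** The strongest reply is that the clause is loosely drafted rather than restrictive. It can be read as covering anyone who is pregnant during the 12 months, whenever this is found. Both section headings speak of becoming pregnant and carry no time limit. Section 5.10.4.2, read alone, has none either, and its cross-reference could be to procedure only. The protocol also treats the Month 12 visit, window included, as its 12-month test, so an investigator with a positive result on day 380 would probably report it. This stands as far as it goes: exclusion is the literal reading, not the only one. But two possible readings of an expedited-reporting trigger are themselves a reason to settle it.

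A reader might infer that nothing else in the protocol would catch these pregnancies. The documents do not support that: the back-stops above exist, and the pregnancy form and safety management plan, which might say more, are not among the documents.

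A reader might also measure the problem by starting from the earliest permitted Month 12 visit, adding an assumed detection lag, and counting the days left untested. That measures test coverage, not the reporting rule. Discovery is not confined to scheduled tests, and changing the reporting clause would leave test coverage as it is.

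Finally, no endpoint or analysis depends on this, and SAP 2.2.3 describes all 34 participants (23 + 11) as already dosed. How many could conceive, or have partners who could, is not stated. The number affected may be very small or nil.

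**Conclusion.** The point holds in a limited form. Followed literally, 5.10.4.3 and 5.10.4.4 leave out pregnancies conceived in the protocol's own 12-month contraception period but found after it, and 21 of the 43 permitted Month 12 visit days fall on the wrong side of the limit. The Month 12 part applies only when the visit is held after the exact 12-month date; a test on or before that date is inside the rule.

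The conclusion rests on the discovery reading of the clause, which is the natural one but not the only one, and on taking 12 months as 365 days. It does not depend on the assumed detection lags, which only illustrate the size of the tail. No number of missed pregnancies can be given. It deserves correction because it concerns safety capture in a study whose primary objective is safety, and because the correction is cheap.

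**What to change.** Reconcile the reporting trigger in 5.10.4.3 and 5.10.4.4 with the 12-month contraception period and the Month 12 visit window. Extend the trigger so that reporting covers:

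1. any pregnancy found in the 12 months after administration, as now; and
2. any pregnancy with an estimated conception date in those 12 months, whenever it becomes known during the study.

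The first limb must stay. A trigger based only on conception after dosing could drop a pregnancy conceived just before administration and found afterwards, which the present wording covers. GP notification and outcome follow-up hang on the same clause, so the sponsor should state how they relate to the extended trigger. The sponsor should also confirm that the pregnancy form captures the estimated conception date; the form is not among the documents, so it may already do so.

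The cost is one added clause in each of two sections, a check of the form, and possibly a few extra reports. Testing and contraception are unchanged.

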# 5.10.4.4 Procedures to follow in the event of the partners of male participants becoming pregnant

Participants are instructed to use double barrier contraception for 12 months after ATIMP administration. However, it is difficult to exclude entirely that the partner of a participant might become pregnant after administration of the ATIMP. In the unlikely event that the partner of a participant is found to be pregnant in the 12 months following ATIMP administration, the participant's GP will be notified that he is participating in a gene therapy trial and that, although the risks involved are minimal, there is a chance of gene transfer to the unborn child. With the participant's consent, we will contact the partner to ascertain the status of the pregnancy and the outcome. The pregnancy will be reported to The PV service provider on a pregnancy report form within 24 hours of the investigator becoming aware of the event, following the instructions on the pregnancy form.

# 5.10.4.5 Investigator responsibilities relating to safety reporting

The Investigator will assume overall responsibility for evaluating and reporting adverse events. In urgent situations another member of the study team may report on their behalf, while making every effort to discuss the event with them. All non-serious AEs and ARs, whether expected or not, should be recorded in the participant's medical notes and reported in the toxicity (symptoms) section of the eCRF. These should be entered on to the database according to the timelines defined in the Data Management Plan to allow appropriate monitoring by the Clinical Management Team (CMT). SAEs and SARs should be notified to the PV service provider immediately after the investigator becomes aware of the event and in no circumstance should this notification take longer than 24 hours.

Clinically significant abnormalities in the results of objective tests will also be recorded as adverse events. If the results are not expected as part of disease or surgery these will also be recorded as unexpected. There are currently no expected events associated with the ATIMP.

All serious adverse events will also be recorded in the hospital notes and the CRF. Adverse events will be recorded with clinical symptoms and accompanied with a simple, brief description of the event, including dates as appropriate. All adverse events will be recorded until the end of the study, or until

pregnancy outcome in the case of pregnancy. All SAEs will be recorded, fully investigated and appropriately managed until resolution or stabilisation and CI sign off.

#### 5.10.4.5.1 Seriousness assessment

When an AE or AR occurs, the investigator responsible for the care of the participant must first assess whether or not the event is serious using the definition given in Table 1. If the event is classified as 'serious' then an SAE form must be completed and emailed to the PV service provider (or delegated body) notified within 1 working day.

#### 5.10.4.5.2 Severity or grading of Adverse Events

The severity of all AEs and/or ARs (serious and non-serious) in this study should be graded using the toxicity gradings in NIH CTCAE Version 4.0 (NIH 2009).

Table2: Grading of Adverse Events

Category	Definition	
Mild (Grade I)	Asymptomatic or mild symptoms; clinical or diagnostic observations only; intervention not indicated	
Moderate (Grade II)	Minimal, local or non-invasive intervention indicated; limiting	
	age appropriate instrumental ADL*	
Severe (Grade III)	Severe or medically significant but not immediately life	
	threatening; hospitalisation or prolongation of hospitalisation	
	indicated; disabling; limiting self-care ADL**	
Grade IV	Life threatening consequences; urgent intervention indicated	
Grade V	Death related to AE	

\* Instrumental ADL (Activities of Daily Living) refer to preparing meals, shopping for groceries or clothes, using the telephone, managing money, etc

#### 5.10.4.5.3 Causality

Causality will be assessed in terms of the ATIMP, the surgical procedures and any of the other procedures in the study. Based on all available information at the time of completion of the case report form, the investigator must assess the causality of all serious events or reactions. It is of particular importance in this study to capture and differentiate events related to:

- The ATIMP administration surgery
- The ATIMP

The differentiated causality assessments will be captured in the study-specific CRF and SAE form using the definitions in Table 3.

Table 3: Causality definitions

Relationship	Description	Event Type
Unrelated	There is no evidence of any causal relationship	Unrelated SAE
Unlikely to be related	There is little evidence to suggest that there is a causal	Unrelated SAE
	relationship (e.g., the event did not occur within a reasonable	

\*\*Self-care ADL refer to bathing, dressing and undressing, feeding self, using the toilet, taking medications, and not bedridden.

	time after administration of study drug). There is another reasonable explanation for the event (e.g., the participant's clinical condition or other concomitant treatment)	
Possibly related	There is some evidence to suggest a causal relationship (e.g., because the event occurs within a reasonable time after administration of study drug). However, the influence of other factors may have contributed to the event (e.g., the participant's clinical condition or other concomitant treatment)	SAR
Probably related	There is evidence to suggest a causal relationship and the influence of other factors is unlikely	SAR
Definitely related	There is clear evidence to suggest a causal relationship and other possible contributing factors can be ruled out.	SAR

#### 5.10.4.5.4 Expectedness

This is a long-term follow-up study to the prior interventional studies, and no intervention is given to participants in this study. Any expectedness assessment will be related to ATIMP and surgery given in the prior interventional study.

Table 4: Assessment of expectedness

Category	Definition
Expected	An adverse event that is classed in nature as serious and which
	is consistent with the information in the Investigator Brochure.
	In view of the very limited clinical experience with the ATIMP
	there are at present no events considered as expected for the
	ATIMP and surgery listed in the current Investigator Brochure.
Unexpected	An adverse event that is classed in nature as serious and which
	is not consistent with the information about the ATIMP and
	surgery listed in the Investigator Brochure*.

\*This includes listed events that are more frequently reported or more severe than previously reported

The reference document to be used to assess expectedness of any SAE related to the ATIMP and/or administrative surgical procedure is the Reference Safety Information (RSI) section of the current Investigator Brochure (IB) for each programme respectively at the time the event started. The RSI section of the IB lists all the expected adverse reactions.

#### 5.10.4.6 Notifications

#### 5.10.4.6.1 Notifications by the Investigator to PV

All adverse events will be recorded in the hospital notes and the CRF.

PV must be notified of all SAEs within 24 hours of the investigator becoming aware of the event. The investigator will respond to any SAE queries raised by the PV provider as soon as possible.

Investigators should notify the PV service provider of any SAE occurring from ICF signature. Any events known to investigator that occur after the end of the study and that may be attributed to ATIMP

administration should be reported to the MHRA using the yellow card system (https://yellowcard.mhra.gov.uk/the-yellow-card-scheme/).

The SAE CRF must be completed by the investigator (the consultant named on the delegation of responsibilities list who is responsible for the participant's care) with attention paid to the grading and causality of the event. In the absence of the responsible investigator, the SAE form should be completed and signed by a member of the site study team and emailed as appropriate within the timeline. The responsible investigator should check the SAE form at the earliest opportunity, make any changes necessary, sign and then email to PV. Systems will be in place at the site to enable the investigator to check the form for clinical accuracy as soon as possible.

The minimum criteria required for reporting an SAE are the study number, patient number, year of birth, name of reporting investigator and sufficient information on the event to confirm seriousness. Any further information regarding the event that is unavailable at the time of the first report should be entered as soon as it becomes available.

The SAE form must be scanned and sent by email to PV service provider as listed on the SAE form.

Participants must be followed up until clinical recovery is complete and laboratory results have returned to normal or baseline values, or until the event has stabilised. Follow-up should continue after completion of study follow-up (i.e., 5 years after delivery of ATIMP) if necessary. Follow-up SAE forms (clearly marked as follow-up) should be completed and emailed to the PV service provider as further information becomes available. Additional information and/or copies of test results etc may be provided separately. The participant's name must not be used on any correspondence and if the name does appear it must be blacked out and replaced with study identifiers on any test results. Any occurrence of a subjects'name must be reported to the clinical trial manager and investigated and remediated to prevent reoccurrence.

